11.2.2 Patient Disposition

The frequency and percentage of patients in each analysis population will be presented. The primary reason for discontinuation of lucitanib will be summarized.

11.2.3 Baseline Characteristics

Baseline characteristics and demographic data will be summarized for the safety population.

11.2.4 Efficacy Analyses

Kaplan-Meier methodology will be used to summarize the time to event variables. The 25th, 50th (median), and 75th percentiles will be presented along with the Kaplan-Meier estimates of the 6 and 12 month rates. The efficacy results may be presented separately by cohort or the three cohorts together.

11.2.4.1 Progression Free Survival (PFS)

PFS is defined as 1+ the number of days from the date of first dose of study drug to disease progression or death due to any cause, whichever occurs first. Patients without a documented event of progression will be censored on the date of their last adequate tumor assessment (i.e., radiologic assessment), or the date of first dose if no tumor assessments have been performed. Progression events will be determined by the investigator. PFS will be summarized utilizing Kaplan-Meier methodology.

11.2.4.2 Objective Response Rate (ORR)

ORR is the proportion of patients with a best response of CR or PR according to RECIST Version 1.1. The best response is recorded from the start of treatment (Day 1) until disease progression or recurrence. The ORR will be summarized with frequencies and percentages.

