
Study Design
	
This is a Phase 2, open-label, multicenter study evaluating the efficacy and safety of lucitanib administered orally to patients with metastatic breast cancer. Patients with metastatic breast cancer will be enrolled into one of two different cohorts (Cohort A: FGF-amplified or Cohort C: FGF non-amplified) both receiving 10 mg daily.
 
For patients with local FGFR1 or 11q test results, a central laboratory will confirm the presence or absence of the FGFR1 or 11q amplification. Central testing prior to enrollment for these patients is not required for study enrollment. Patients with local FGFR1 and 11q results for whom central reading does not confirm amplification status can continue the study at the discretion of the investigator if clinical benefit is observed. If there are a significant number of patients with discordant local and central testing results, additional patients may be enrolled.
 
For patients without a local FGFR1 or 11q test result, tissue must be submitted for central testing under a prescreening process. Under the prescreening process, a confirmed central laboratory test result is required for screening and enrollment into Cohort A (FGFR1- or 11q-amplified) or enrollment into Cohort C (FGF non-amplified).
 
Up to 20 enrolled patients will participate in a PK sub-study to assess the comparative PK of the lucitanib tablet formulation with the lucitanib capsule formulation.
 
Cycles are defined as 28 days in duration. Protocol-specified treatment will continue until there is clinical tumor progression or unacceptable toxicity. Patients will undergo serial assessments for anti-tumor efficacy, drug safety, and PROs. Sparse blood sampling for POPPK analyses will be conducted in all patients treated with lucitanib. Tumor scans will be acquired by the investigative site and evaluated locally for patient treatment decisions. Patients who provide additional consent will undergo an optional post-treatment biopsy for PD analyses.
 
AEs will be assessed from the time of first dose of lucitanib through 28 days after the last protocol-specified treatment administration. For the first 6 cycles, patients will undergo tumor scans within 28 days prior to the first drug administration, 4 weeks after first drug administration, and every 8 weeks thereafter. Patients with stable disease or better after their Cycle 6 scan will continue to have tumor scans every 12 ± 1 weeks until tumor progression. All patients will be followed at approximately two monthly intervals to determine survival status, until death or sponsor decision to end the trial, whichever comes first. After discontinuation of protocol-specified treatment, subsequent anticancer therapy use will be recorded.

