4 STUDY OBJECTIVES AND ENDPOINTS

4.1 Objectives

4.1.1 Primary Objective

- To estimate the anti-tumor efficacy of oral single-agent lucitanib as measured by investigator assessed PFS, when administered to patients with *FGFR1*- or 11q-amplified breast cancer after failure of currently available standard therapies

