4.1.2 Secondary Objectives

- To estimate anti-tumor efficacy of oral single-agent lucitanib as measured by ORR, DR, disease control rate (DCR), and OS To estimate patient-reported outcomes (PRO) following treatment with lucitanib
- To evaluate safety and tolerability of lucitanib
- To assess the comparative PK of the lucitanib tablet formulation with the lucitanib capsule formulation

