9.5.2 Efficacy Evaluations

9.5.2.1 Tumor Assessments

The first on-treatment scan should be completed on Cycle 2, Day 1, and every 8 ± 1 weeks through Cycle 6 (i.e., C4D1, C6D1). Thereafter, scans should be completed every 12 ± 1 weeks (i.e., C9D1, C12D1, C15D1, etc.) until disease progression. All patients must have scans to confirm radiographic progression. Tumor scans do not need to be repeated at end-of-study if <2 weeks since last scan or the patient had disease progression at the last scan. Patients that permanently discontinue lucitanib should continue scans until radiographic disease progression. Scans will be evaluated locally for patient treatment decisions. Copies of tumor scans will be

collected centrally to facilitate independent evaluation if subsequently required. Tumor response will be interpreted using RECIST Version 1.1 ([Appendix A](#)).

Tumor assessments should consist of clinical examination and CT scans of the chest, abdomen, and pelvis with intravenous contrast and appropriate slice thickness per RECIST Version 1.1; other alternative studies (MRI and X-ray) may be performed if clinically indicated. The same methods used to detect lesions at baseline are to be used to follow the same lesions throughout the clinical study.

Brain imaging is required at baseline. Patients with brain lesions detected at baseline require repeat brain imaging as part of the follow-up tumor assessments. The same methods used to detect brain lesions at baseline are to be used to follow the lesions throughout the clinical study.

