11.2.4.4 Disease Control Rate (DCR)

The DCR is defined as the percentage of patients with a best response rate of CR, PR, or SD for at least 12 weeks. The DCR will be summarized with frequencies and percentages.

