The best overall response is the best response recorded from the start of the study treatment until the end of treatment taking into account any requirement for confirmation. On occasion a response may not be documented until after the end of therapy so protocols should be clear if post-treatment assessments are to be considered in determination of best overall response. Protocols must specify how any new therapy introduced before progression will affect best response designation. The patient's best overall response assignment will depend on the findings of both target and non-target disease and will also take into consideration the appearance of new lesions. Furthermore, depending on the nature of the study and the protocol requirements, it may also require confirmatory measurement. Specifically, in nonrandomized trials where response is the primary endpoint, confirmation of PR or CR is needed to deem either one the 'best overall response'.

Time point response

It is assumed that at each protocol specified time point, a response assessment occurs. [Table 8](#) below provides a summary of the overall response status calculation at each time point for patients who have measurable disease at baseline.

Table 8: Evaluation of best overall response: patients with measurable and non-measurable disease			
Target Lesions	Non-target Lesions	New Lesions	Overall Response
CR	CR	No	CR
CR	Non-CR/non-PD	No	PR
CR	Not evaluated	No	PR
PR	Non-PD or not evaluated	No	PR
SD	Non-PD or not evaluated	No	SD
Not all evaluated	Non-PD	No	NE
PD	Any	Yes or No	PD
Any	PD	Yes or No	PD
Any	Any	Yes	PD

NE = Not evaluable.

When patients have non-measurable disease only (therefore non-target), the following table is to be used.

Table 9: Evaluation of best overall response: patients with non-measurable disease		
Non-target Lesions	New Lesions	Overall Response
CR	No	CR
Non-CR/non-PD	No	On-CR/non-PD ¹
Not all evaluated	No	NE
Unequivocal PD	Yes or No	PD
Any	Yes	PD

NE = not evaluable.
1 = 'Non-CR/non-PD' is preferred over 'stable disease' for non-target disease since SD is increasingly used as endpoint for assessment of efficacy in some trials so to assign this category when no lesions can be measured is not advised.

Missing assessments and inevaluable designation

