#### 12.1.2 Objective Response Rate (ORR)

ORR is the proportion of patients with a best response of CR or PR according to RECIST Version 1.1. The best response is recorded from the start of treatment (Day 1) until disease

progression or recurrence. The ORR will be summarized with frequencies and percentages. The number and frequency of confirmed responses (CR+PR) will also be tabulated.

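### Best response has no cut-off at new anticancer therapy, so under the written rule a next-line response would count in ORR and DCR for single-agent lucitanib

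*Protocol*

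**What the plan says.** Protocol 11.2.4.2 sets the ORR window: "The best response is recorded from the start of treatment (Day 1) until disease progression or recurrence". SAP 12.1.2 uses the same one ("The best response is recorded from the start of treatment (Day 1) until disease" and so on to progression or recurrence) and adds a count of confirmed responses without a different window. DCR, in Protocol 11.2.4.4 and SAP 12.2.2, is the "percentage of patients with a best response rate of CR, PR, or SD for at least 12 weeks" and has no window of its own.

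Scanning does not stop with the drug. Protocol 9.5.2.1 says: "Patients that permanently discontinue lucitanib should continue scans until radiographic disease progression"; the Synopsis says the same. Later treatment is captured: "After discontinuation of protocol-specified treatment, subsequent anticancer therapy use will be recorded" (Synopsis, and similarly Protocol 5.1.2, 9.3 and 9.4). No efficacy definition in either document uses that record.

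The objective behind these endpoints, Protocol 4.1.2, is "To estimate anti-tumor efficacy of oral single-agent lucitanib as measured by ORR, DR, disease control rate (DCR), and OS". Appendix A, which Protocol 9.5.2.1 names for interpreting response, ends the best-response window when treatment ends. It also warns: "Protocols must specify how any new therapy introduced before progression will affect best response designation".

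**The concern.** A patient may have stable disease on lucitanib, stop for toxicity, start chemotherapy and reach a partial response before any progression is recorded. Under Protocol 11.2.4.2 and SAP 12.1.2 that patient is a responder in an estimate described as single-agent lucitanib.

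Such patients are foreseeable. The protocol provides for stopping without RECIST progression because of toxicity (7.4), non-compliance (7.7) or investigator decision (12.1). Treatment also ends at clinical progression (5.1.2), while Appendix A treats symptomatic deterioration as a reason for stopping and not as an objective response.

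There is no control arm, so a misattributed response cannot be told apart from lucitanib activity. The two windows also conflict: one programmer working from 11.2.4.2 and another from Appendix A could derive different ORRs from the same data.

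**Working it through.** **The plan's own figures.** No precision figure is given for ORR or DCR. The only sizing figures concern the 6-month PFS rate (Protocol 11.3). With a normal-approximation 90% interval ignoring censoring, 1.645 × √(0.50 × 0.50 / 80) = 9.2 points, giving 40.8% to 59.2%. For 40 patients at 25%, the half-width is 11.3 points and the upper limit 36.3%. Both stated claims reproduce, but they do not bear on this point, which rests on the definitions.

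**The definitions side by side.**

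| Item | Window ends at | Stops at new therapy? |
|---|---|---|
| ORR, Protocol 11.2.4.2 and SAP 12.1.2 | progression or recurrence | no |
| DCR, Protocol 11.2.4.4 and SAP 12.2.2 | not stated; uses best response | no |
| DR, Protocol 11.2.4.3 and SAP 12.2.1 | documented progression | no |
| Best overall response, Appendix A | end of treatment | left to the protocol |

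**Direction.** Best response is the best category over the window. With the denominator fixed, a longer window can add a responder but never remove one, so the error in ORR cannot be downward. The same holds for DCR.

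**Size for ORR.** The documents give none of the inputs, so all three are assumptions:
- true lucitanib ORR, b = 20%;
- share of patients stopping before progression and starting new therapy, q = 5% to 20%, independent of response;
- next-line response rate, r = 20% to 30%.

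A patient who already responded on lucitanib adds nothing, so the inflation is (1 − b) × q × r:
- low: 0.80 × 0.05 × 0.20 = 0.8 points;
- middle: 0.80 × 0.10 × 0.25 = 2.0 points;
- high: 0.80 × 0.20 × 0.30 = 4.8 points.

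Relative to 20%, that is an overstatement of 4% to 24%. In 80 patients it is 0.6 to 3.8 responders, each worth 1/80 = 1.25 points.

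**DCR.** Scans fall at about weeks 4, 12 and 20. A patient with stable disease at week 4 whose last dose is at week 8 has the End-of-Study visit 28 ± 7 days later, at weeks 11 to 13. That scheduled scan can complete the 12 weeks even if a new drug has already started. As a loose illustration, let 5–20% of all patients stop before week 12 with neither progression nor response and start new therapy, and let 30–70% of these be controlled at week 12. DCR then rises by 0.05 × 0.30 = 1.5 points to 0.20 × 0.70 = 14 points. The upper end is generous, since it needs a fifth of patients to switch within 12 weeks.

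**The case against.** The strongest objection is that few off-drug scans may exist. Protocol Tables 4 and 5 mark scans at screening, on treatment and at End-of-Study, and none in the two-monthly follow-up. Section 9.4 lists only survival and later therapies, 12.1 describes telephone contact for survival, and 5.1.3 treats the trial as complete after the End-of-Study visit. A scan 28 ± 7 days after the last dose leaves little time for a next-line partial response. This stands as a reason to expect a smaller effect on ORR. It does not remove the problem: 9.5.2.1 and the Synopsis still call for scans until radiographic progression, so the documents disagree about how long scanning lasts.

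Second, Appendix A's shorter window would exclude next-line responses. But that text is a general RECIST summary that passes the question of new therapy to the protocol, and the SAP carries forward the longer window. It adds a conflict and does not settle the matter.

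Third, Protocol 8.1.2 prohibits other systemic anticancer therapy. That is a concomitant-medication rule; 5.1.2 and 9.4 expect further therapy after discontinuation.

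Fourth, several features pull the size down. Protocol 3.6.1.3 describes discontinuation for adverse events as uncommon. A partial response must be a 30% fall from the pre-lucitanib baseline. Patients with only non-measurable disease, who are eligible, cannot be classed as partial responders (Appendix A, Table 9). These points stand. Confirmation would not filter such responses out: Appendix A does not require it, and the SAP's confirmed-response count has no cut-off either.

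**Conclusion.** The rule as written, in both documents, would credit a response on the next therapy to single-agent lucitanib, and Appendix A contradicts it without resolving it. The bias in ORR is upward only. On the assumptions shown it is about 0.8–4.8 points and may be smaller, given the visit schedule. DCR moves the same way; its illustrative range shows sensitivity to assumptions and is not an estimate. The wording gap is certain; its size is not.

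A reader might infer three stronger things that the documents do not support:
- *That next-line responses will in fact be counted in number.* The documents give neither the share of patients switching before progression nor a settled scan schedule after End-of-Study.
- *That ORR is inflated by 1.0–6.0 points*, from q × r alone (0.05 × 0.20 to 0.20 × 0.30). That requires every patient who switches to be a non-responder on lucitanib, which nothing in the documents establishes.
- *That the primary endpoint is compromised.* The primary objective is "To estimate the anti-tumor efficacy of oral single-agent lucitanib as measured by investigator assessed PFS". Counting progression or death regardless of later therapy is a legitimate and explicit PFS definition. The stated criteria in Protocol 11.3 are median and 6-month PFS; ORR and DCR carry no threshold.

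This should be corrected before database lock, as a bias of known direction in secondary endpoints.

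**What to change.** 1. **ORR (Protocol 11.2.4.2, SAP 12.1.2):** make the window run from Day 1 to disease progression or the start of subsequent anticancer therapy, whichever comes first. Apply it also to the SAP's confirmed-response count.
2. **DCR (Protocol 11.2.4.4, SAP 12.2.2):** these sections have no window to edit, so add a sentence that only assessments inside the ORR window count, including those used to establish 12 weeks of stable disease.
3. **DR (Protocol 11.2.4.3, SAP 12.2.1):** count only responses first recorded inside the window. State that patients who start new therapy before progression are censored at the last adequate scan before it. Censoring calls for the Kaplan-Meier summary that the protocol specifies, in place of the SAP's descriptive statistics.
4. **Appendix A:** align its best-response window with item 1.
5. **Data:** confirm that the eCRF holds start dates of subsequent therapy. The documents say that later therapies are recorded but do not mention dates.
6. **PFS:** leave the definition as it is. A sensitivity estimate censoring at new therapy is optional.

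The cost is wording in two documents, a check of the eCRF and, if wanted, one extra PFS table. If start dates were not collected, they would have to be queried. The downside is that ORR and DCR may be slightly less favourable.

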11.2.4.3 Duration of Response (DR)

DR for CR and PR will be measured from the date that any of these best responses is first recorded until the first date that PD is objectively documented. DR will be summarized utilizing Kaplan-Meier methodology.

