After the end of the treatment, the need for repetitive tumor evaluations depends on whether the trial has as a goal the response rate or the time to an event (progression/death). If ‘time to an event’ (e.g., time to progression, disease-free survival, PFS) is the main endpoint of the study, then routine scheduled re-evaluation of protocol specified sites of disease is warranted. In randomized comparative trials in particular, the scheduled assessments should be performed as identified on a calendar schedule (for example: every 6–8 weeks on treatment or every 3–4 months after treatment) and should not be affected by delays in therapy, drug holidays, or any other events that might lead to imbalance in a treatment arm in the timing of disease assessment.

Confirmatory Measurement/Duration of Response

Confirmation

As ORR is not the primary endpoint, confirmation of response is not required.

Duration of Overall Response

The duration of overall response is measured from the time measurement criteria are met for CR or PR (whichever is first recorded) until the first date that recurrent or PD is objectively documented (taking as reference for PD the smallest measurements recorded since the treatment started).

The duration of overall CR is measured from the time measurement criteria are first met for CR until the first date that recurrent disease is objectively documented.

Duration of Stable Disease

SD is measured from the start of the treatment (in randomized trials, from date of randomization) until the criteria for progression are met, taking as reference the smallest measurements recorded since the treatment started (if the baseline sum is the smallest, this is the reference for calculation of PD).

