## **12.2** Key Secondary Efficacy Analyses

### 12.2.1 Duration of Response (DR)

DR for CR and PR will be measured from the date that any of these best responses is first recorded until the first date that PD is objectively documented. DR will be summarized using descriptive statistics (N, mean, standard deviation, median, minimum, and maximum).

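### Duration of response has no rule for responders who die without documented progression, and the protocol and SAP summarise it by conflicting methods

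*Protocol*

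**What the plan says.** **End of DR.** Protocol 11.2.4.3 has DR "measured from the date that any of these best responses is first recorded until the first date that PD is objectively documented". SAP 12.2.1 likewise runs it "until the first date that PD is objectively documented". Death is not mentioned, and neither section says what happens to a responder who never has a progression date.

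**PFS for comparison.** Protocol 11.2.4.1 ends PFS at "disease progression or death due to any cause, whichever occurs first", with a stated censoring rule. SAP 12.1.1 uses the same events.

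**Summary method.** The protocol states that "DR will be summarized utilizing Kaplan-Meier methodology". SAP 12.2.1 states that "DR will be summarized using descriptive statistics (N, mean, standard deviation, median, minimum, and maximum"). SAP 16.1 adds that missing data are not imputed.

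**Appendix A of the protocol.** Here DR runs as follows: "measured from the time measurement criteria are met for CR or PR (whichever is first recorded) until the first date that recurrent or PD" (the sentence goes on to require objective documentation). Its end point also leaves out death, and adds recurrence to progression.

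**The concern.** DR is a named secondary endpoint, and the rationale for the study rests partly on durability of benefit. As defined, it leaves three things open.

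- A responder who dies before a scan shows progression counts as a failure for PFS but not for DR.
- The two documents prescribe summaries that treat responders without a progression date in incompatible ways. Kaplan-Meier can hold them as censored; a mean and standard deviation cannot.
- The clock starts when one of the patient's *best* responses is first recorded. Protocol 11.2.4.2 uses best response for the patient's single best category. For a patient who has PR and later CR, a programmer could therefore start at the CR date, while Appendix A starts at the PR date.

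Two analysts following these texts could report different DR values from the same data.

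**Working it through.** The documents state no planned DR estimate, event count or precision, so there is no figure to reproduce. The size of the effect has to be illustrated.

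**Inputs**

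- q, the share of first DR terminations (progression or death) that are deaths without documented progression: not in the documents; 5% to 20% assumed.
- Scale: a mean DR of 7.6 months in the earlier phase 1/2 study (Protocol 3.6.1.2), used here only as an assumed mean time to progression or death.
- Scan spacing: 8 weeks through Cycle 6, then 12 weeks (Protocol 9.5.2.1).

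**1. Direction under the protocol's Kaplan-Meier.** The estimate is the product of (1 − dᵢ/nᵢ) over event times. Recoding a death as censored on its own date lowers dᵢ and leaves every nᵢ unchanged, so the curve stays the same or rises. Suppose instead the patient were censored at the last scan before death, with n at risk then and k progressions between scan and death. The step over that stretch is (n−1−k)/(n−1) rather than (n−1−k)/n. The curve may dip marginally before the death date, but is at least as high from then on.

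**2. Size under constant hazards.** With total hazard λ, the progression hazard is λ(1−q).

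- Median counting death: ln 2/λ
- Median with deaths censored: ln 2/[λ(1−q)]
- Ratio: 1/(1−q), whatever λ is

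With 1/λ = 7.6 months, the median counting death is 0.693 × 7.6 = 5.27 months.

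| q (assumed) | Ratio | Median, deaths censored | Simulated: deaths censored vs counted |
|---|---|---|---|
| 5% | 1/0.95 = 1.053 | 5.55 | 5.52 vs 5.23 |
| 10% | 1/0.90 = 1.111 | 5.85 | 5.86 vs 5.27 |
| 20% | 1/0.80 = 1.250 | 6.58 | 6.57 vs 5.25 |

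The simulation used 200,000 responders per row, independent exponential times, and follow-up ending uniformly between 6 and 24 months.

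**3. The SAP's descriptive statistics.** The same simulated responders were used, restricted to those with a progression date. For all three values of q the median was about 4.05 months and the mean about 5.13. The values counting death are 5.27 and 7.6. The median is therefore 1 − 4.05/5.27 = 23% too low and the mean 1 − 5.13/7.6 = 32% too low, because long responses still running at cutoff drop out. If every responder is instead assigned the last observed time, whether progression, death or cutoff, the mean is about 6.27 months, still short of 7.6. The direction is the reverse of step 2.

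**4. Start date.** Only PR-then-CR patients are affected. Starting at CR removes at least one nominal scan interval: 56/30.44 = 1.84 months at 8-week spacing, or 84/30.44 = 2.76 months at 12-week spacing. This shortens DR.

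**The case against.** **The end point follows the protocol's own criteria.** DR is declared to be according to RECIST 1.1, and Appendix A, the protocol's summary of those criteria, also ends without death. This stands: on death, the body and the appendix do not conflict. Adding death is a change of convention that brings DR into line with PFS. But no other section supplies the missing rule either.

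**A reader might infer that DR as planned is overstated.** The documents do not support that without conditions. Nowhere do they say that deaths without progression are censored. That follows only if Kaplan-Meier is used, as the protocol says. The SAP, which fixes the final analysis, specifies a summary with no censoring, and step 3 shows that it can understate DR.

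**A reader might infer that the start date contradicts Appendix A.** It need not. The body wording can be read as whichever of CR or PR is recorded first, which is what Appendix A says. It is ambiguous, and the divergent reading would shorten DR.

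**Such deaths may be few.** Scans are to continue after lucitanib is stopped, until radiographic progression (Protocol 9.5.2.1), which limits q. On the other side, scans are up to 12 weeks apart, treatment may stop for clinical progression (Protocol 5.1.2), and Appendix A does not accept symptomatic deterioration as objective progression. The documents do not settle how large q is.

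**Little hangs on DR.** This stands too. The criteria for further study and for Cohort C rest on PFS (Protocol 11.3, SAP 3), DR carries no test or threshold, and PFS and OS both count deaths.

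**Conclusion.** The point holds as a gap in the event definition, a missing censoring rule and a conflict of method between the two documents. It does not hold as a bias of known direction. If the protocol's Kaplan-Meier is used and deaths without progression are censored, the median is inflated by about 5% to 25%. That range rests on constant, independent hazards and on an assumed q of 5% to 20%; a smaller q gives less. If the SAP's descriptive statistics are used on responders with a progression date, DR tends to be understated.

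The 7.6-month figure sets the scale only. It is a mean, and the protocol does not say how deaths were handled in it. It should not be multiplied by a ratio of medians or taken as a like-for-like benchmark.

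The start date is a matter of clarification. The consequence is confined to a descriptive secondary endpoint, but the correction is cheap and should be made before database lock.

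**What to change.** Use one definition in Protocol 11.2.4.3 and SAP 12.2.1:

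> DR is the time from the first recorded CR or PR, whichever is earlier, to the first documented PD or recurrence, or death from any cause. Responders with none of these are censored at the last adequate tumour assessment. DR is summarised by Kaplan-Meier.

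In SAP 12.2.1 this must replace the descriptive statistics. If the mean and standard deviation stay, the censoring rule has nothing to act on. Appendix A needs death added to its end point so that it matches.

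The cost is a short replacement in each of the two sections and the matching line in the appendix. No new data are needed, because survival is already followed about every two months (Protocol 5.1.4). The price is that reported DR may be slightly shorter than under a progression-only Kaplan-Meier analysis.
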